## 7.0 Expected risk and benefits

**Risks: Blood draws:** Blood drawing may cause temporary discomfort from the needle stick, bruising, and infection. A total of 18 blood samples (20 ml each) will be collected over 24 weeks = 360 ml total.

**Alternate day fasting:** Alternate day fasting is generally well tolerated and has no harmful effects. Subjects may feel hungry, however, which is unpleasant. **DXA scans:** DXA scans will be performed to assess body composition (3 scans total). Subjects who participate in this study will receive a small amount of radiation from the DXA scanning. The amount is similar to that received in many standard x-ray procedures, but is considerably more than subjects would receive from natural daily exposure or in the normal course of treatment, and it carries at least a theoretical risk. **Magnetic resonance spectroscopy (MRS):** There are no known hazards to MRS examination other than the discomfort associated with confinement and remaining stationary for the duration of the study. Testing of all subjects will be terminated immediately should they become distressed. We will carefully screen out individuals who have an implanted electrical device (such as a cardiac pacemaker or a neurostimulator), or a certain type of metallic clip (i.e., an aneurysm clip in the brain). These devices can malfunction and cause harm to the patient in the magnet environment. We will also carefully screen individuals who are claustrophobic to reduce any adverse events. **Confidentiality:** To protect subject identity, only code numbers (i.e. randomly generated numbers) will identify all laboratory specimens, evaluation forms, reports, and other records. **Exercise program:** Risks of participating in the

exercise program include: muscle/joint strains, sprains, or injury. If a subject is injured during the exercise session, they will be asked to stop exercising immediately and rest. The muscle/joint will be iced and elevated, and the subject will be sent home with a small ice pack and asked to ice/elevate the area for 20 minutes every hour to alleviate pain and inflammation. The subject will refrain from participating in the exercise session until the pain has significantly improved. If the pain does not improve in 48 hours, it will be recommended that the subject follow-up with their doctor. A cardiac event may also occur as a result of participating in the exercise program. If this occurs, 911 will be immediately called by the research assistant who is supervising the exercise session and the subject will be treated by a medical professional.

**Risk of coercion:** Some subjects will be recruited from the Hepatology Clinic at the University of Illinois Medical Center by [name] MD (Co-investigator). Thus, there is a risk that subjects may feel coerced by [name] to participate in the research. To mitigate this, each subject will be clearly informed that they are not obligated to participate in this research study offered by [name]. Subjects will also be informed that participating in the study is completely voluntary and they are free to not participate. They will also be told that their decision to not participate will not affect your clinical care now or in the future.

**Benefits:** Subjects may lose weight as a result of treatment. Since weight loss has been shown to improve some metabolic disease risk factors, subjects partaking in the treatment may experience these benefits to their overall health. No benefits can be guaranteed, however.

## 8.0 Data collection and management procedures

Sources of data include body weight and body composition measurements, hepatic steatosis measurement by MRS, hepatic insulin sensitivity by OGTT, blood pressure measurements, biochemical analyses of blood draws, activity monitor measurements, and questionnaire responses. Questionnaires will be stored in locked filing cabinets at the HNRU. To protect subject identity, code numbers only will identify all laboratory specimens, evaluation forms, reports, and other records. Subject identities will not be used in any reports or publications resulting from this study. All patient records will be kept in locked files; code sheets linking the patient's name to a patient identification number will be stored separately in a locked file cabinet. Only study personnel will have access to the files. Blood specimens will be stored at the HNRU in a locked -80C freezer. Specimens will not be labeled with any personal identifiers. Only the subject ID and study week will be on the label of the blood specimens. Code sheets linking the patient's name to a patient identification number will be stored separately in a locked file cabinet.

## 9.0 Data analysis

Data will be analyzed by [name] PhD (Biostatistician) and [name] by SPSS software (SPSS v24).

## 10.0 Quality control and quality assurance

The PI will be responsible for the evaluation of data quality, and this will be done on a weekly basis by evaluating biochemical analyses output and reviewing questionnaire responses.

## 11.0 Data and safety monitoring

**Assessment of Risk:** The risk of significant adverse events to participants in this study is low. During the 24-week study, participants will undergo 18 blood draws, 3 DXA scans, 3 MRS scans, alternate day fasting and exercise.

**Anticipated Adverse Events:** Blood drawing may cause temporary discomfort, bleeding or bruising at the needle site and in rare cases fainting and infection. As for the DXA scan, the radiation dose associated with DXA measurements is very low or even insignificant in comparison with background radiation levels. Subjects may feel hungry as a result of the ADF diet, which may be unpleasant. Other forms of psychological stress may result from the dietary restriction or the demands of participating in and complying with a study. The subjects will be clearly informed of the expectations of the study at their

screening appointment (e.g. dietary protocol, exercise intervention, time commitment, etc.), and will be free to withdraw from the study at any point. There are no known hazards to MRS examination other than the discomfort associated with confinement and remaining stationary for the duration of the study. Testing of all subjects will be terminated immediately should they become distressed. We will carefully screen out individuals who have an implanted electrical device (such as a cardiac pacemaker or a neurostimulator), or a certain type of metallic clip (i.e., an aneurysm clip in the brain). These devices can malfunction and cause harm to the patient in the magnet environment. We will also carefully screen individuals who are claustrophobic to reduce any adverse events. Loss of confidentiality may also be a risk. To protect subject identity, only code numbers (i.e. randomly generated numbers) will identify all laboratory specimens, evaluation forms, reports, and other records. Risk of participating in the exercise program includes: muscle/joint strains, sprains, or injury. If a subject is injured during the exercise session, they will be asked to stop exercising immediately and rest. The muscle/joint will be iced and elevated, and the subject will be sent home with a small ice pack and asked to ice/elevate the area for 20 minutes every hour to alleviate pain and inflammation. A cardiac event may also occur as a result of participating in the exercise program. If this occurs, 911 will be immediately called by the research assistant who is supervising the exercise session and the subject will be treated by a medical professional.

**Adverse Event Grading Scale:** Because only minor adverse events related to blood drawing, DXA scanning, MRS scanning, alternate day fasting and exercise may occur, no grading scale is necessary.

**Reporting of Adverse Events:** Reporting of adverse events will follow requirements mandated by the University of Illinois Office for Protection of Research Subjects (OPRS) and the NIH. The OPRS will receive a verbal or e-mail report of any serious adverse event (SAE) that occurs during the conduct of the study within 48 hours. This will be followed by a detailed written report within 10 working days. In addition, any incidents or problems involving the conduct of the study or patient participation, including problems with the recruitment and/or consent processes will be reported within 10 working days. The NIH Program Official will be provided with a detailed written report of fatal, life threatening SAEs and unanticipated problems (UP) within 7 calendar days of the event. The NIH Program Official will be notified of any UPs that pose greater risk of harm to study participants than was previously known or recognized within 30 calendar days of the event.

**Safety Monitoring Plan:** Sterile procedures will be employed for all blood drawing procedures. Subjects will be provided with a 24-hour contact phone number to report any persistent problems. The OPRS will be notified of any adverse events as described above.

**Frequency of Safety Reviews:** Safety reviews will be conducted annually in conjunction with the protocol renewal to OPRS.

**Persons to Perform Safety Reviews:** The PI will be responsible for reporting any adverse events and conducting the annual safety review of study data.

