### **Exercise protocol**

[figure not shown]
**Exercise group and combination groups:** Only combination and exercise groups will partake in the exercise training. All training sessions will be conducted at the subject's home. Subjects will participate in a supervised aerobic exercise program 5 times per week, 40-60 min/d, for 24 weeks. Exercise will be performed by watching YouTube aerobic exercise (Zumba) videos at home. The video links will be provided by the study coordinator prior the exercise session. The coordinator conducting the study session on Zoom will have immediate knowledge of the subject's location so that they can relay this information to emergency personnel if needed. During the week 1 sessions, subjects will exercise for 40 minutes at a moderate intensity (65% heart rate max (HRmax)). During the week 2 sessions, subjects will train for 50 minutes at a higher intensity (75% HRmax). For weeks 3-24, subjects will train for 60 minutes at an even higher intensity (85% HRmax). The participants will wear heart rate monitors (Fitbit Alta HR, Boston, MA) during each training session to provide visual feedback of their individualized target heart rate. Fitbit monitors will be distributed to subjects so that they can monitor their heart rate at home. **Compliance with the training:** A research assistant will be present to supervise all the training sessions over Zoom. All sessions will be pre-scheduled with the research assistant so the participant knows when to enter the Zoom meeting to perform the activity. Exercise will be carefully documented through regular online attendance at the training sessions. Subjects will be permitted to choose the day and time slot that works best for them. If a subject misses their session, they will be required to make up for it that same week. Subjects will be permitted to miss 5 sessions total during the 24-week trial.

**ADF group and control groups:** ADF and control subjects will be asked to maintain their regular daily activity habits during the study. They will not participate in the exercise protocol.

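### Adverse-event grading is waived on a premise that Section 11.0 itself contradicts, and events are likely to be less closely observed in the two arms without exercise

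*Combined protocol and SAP*

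**What the plan says.** Section 11.0, under Adverse Event Grading Scale, gives one reason for having no scale, namely that nothing beyond minor events is expected from the study procedures or the interventions: "alternate day fasting and exercise may occur, no grading scale is necessary".

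Other text on harms:

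- The paragraph just before the waiver states: "A cardiac event may also occur as a result of participating in the exercise program". The response is that "911 will be immediately called by the research assistant who is supervising the exercise session". Section 7.0 repeats both statements.
- The Assessment of Risk paragraph says: "The risk of significant adverse events to participants in this study is low".
- Under Reporting of Adverse Events, the university's research-protection office (OPRS) hears of any serious adverse event (SAE) within 48 hours, with a written account within 10 working days. The NIH receives a "detailed written report of fatal, life threatening SAEs and unanticipated problems (UP) within 7 calendar days of the event".
- Safety review is annual and is done by the principal investigator.

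On how events come to notice:

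- Section 6.0, Exercise protocol, says of the exercise and combination arms: "A research assistant will be present to supervise all the training sessions over Zoom". The ADF and control arms have no sessions.
- The Control group protocol in Section 6.0 equalizes research-center visits for outcome measurement only.
- The route by which participants in any arm can report a problem is in the Safety Monitoring Plan: "Subjects will be provided with a 24-hour contact phone number to report any persistent problems".

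**The concern.** An explicit rule in the safety plan rests on a reason that the plan's own text refutes. This goes beyond missing detail. The protocol considered grading and ruled it out, on a premise that cannot stand beside an anticipated cardiac event or the timelines for fatal events.

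The population makes severity worth recording. Eligible participants are sedentary, with BMI up to 59.9 kg/m², and two arms train at 85% of maximum heart rate from week 3. Without grades, a run of moderate injuries and a run of trivial ones look the same at the annual review unless one of them meets the definition of serious.

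Uneven observation adds to this. Staff are present live, many times, in two arms, while the other two depend mainly on participants choosing to call. If anyone later sets event counts side by side by arm, part of any excess in the exercise arms could come from closer watching, and harms of fasting alone could be under-recorded.

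**Working it through.** The plan states no figure on this point, so there is none to reproduce. The check compares the text and then counts scheduled contacts.

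**1. Does the premise hold?** The waiver requires that exercise-related events can only be minor. Section 11.0 says a cardiac event may result from exercise and would prompt a 911 call, and Section 7.0 agrees. The risk of significant events is called low, which is not the same as absent. The reporting rules cover fatal and life-threatening SAEs. All of this text is incompatible with the premise, and no other reason for the waiver is offered.

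**2. What does the waiver remove?** Seriousness and severity are separate classifications. The SAE rules keep seriousness, with reference to OPRS and NIH requirements. Severity is the part that is dropped. The gap therefore covers events that are not serious, or whose seriousness is debatable.

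**3. Is there systematic capture elsewhere?** The study activities table has no adverse-event row. Section 8.0 does not list adverse events among the data sources. Section 10.0 describes a weekly check of biochemical output and questionnaires. Section 12.0 has no harms analysis.

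**4. How unequal is the opportunity to observe?** Inputs from Section 6.0: 5 sessions a week, 24 weeks, 5 permitted misses, common outcome assessments at weeks 1, 13 and 24, and one dietitian meeting described for the two ADF arms.

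- Sessions: 5 × 24 = 120; after permitted misses, 120 − 5 = 115.
- Observed time at full attendance: 5 × 40 + 5 × 50 + 22 × 5 × 60 = 200 + 250 + 6,600 = 7,050 minutes, or 117.5 hours. The ADF and control arms have none.
- Contact ratio = (common contacts + sessions) / common contacts:
  - Exercise against control, 3 common contacts: (3 + 115)/3 = 39.3 to (3 + 120)/3 = 41.0.
  - Combination against ADF, adding the dietitian meeting: (4 + 115)/4 = 29.8 to (4 + 120)/4 = 31.0.
  - Exercise against control, assuming two visit days per time point: (6 + 115)/6 = 20.2 to (6 + 120)/6 = 21.0. The 18 blood samples suggest this reading: 18/3 = 6 per time point, against 5 used by the glucose tolerance test.
  - Exercise against control, assuming all 24 weekly home weights are staff contacts in both arms: (24 + 115)/24 = 5.8 to (24 + 120)/24 = 6.0.

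**5. Can this be turned into a bias?** If the true event rate r were equal in two arms with capture probabilities c₁ and c₂, the recorded ratio would be (r × c₁)/(r × c₂) = c₁/c₂. The documents give neither capture probability, and contact counts do not stand in for them. The likely direction is over-representation of events in the exercise arms. The size is unknown.

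**The case against.** The strongest reply is that the wording is careless but the safeguards are intact. A cardiac event would be reported through the SAE rules without any grade. People with known cardiovascular, pulmonary or renal disease are excluded, and intensity rises in steps from 65% to 75% to 85% of maximum heart rate. Supervision is placed where the exercise risk arises. No aim or analysis compares harms between arms. Adverse-event handling also follows OPRS and NIH requirements, which are not in the documents, and the case report forms are not included.

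Much of this stands, and it rules out three stronger readings that a reader might infer:

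- *That the annual review could not tell a strain from a serious event.* The SAE rules still separate serious events.
- *That the trial is blind to events in the ADF-only and control arms.* Both have the phone line and the same outcome visits, and Section 13.3 provides for informing participants whose laboratory risk values worsen.
- *That detection differs about 40-fold.* That figure counts scheduled contacts on one reading and falls to about 6 on another. No text says that staff ask about or record adverse events at sessions, although it does describe staff responding there to a cardiac event.

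The reply does not rescue the waiver. Its only stated reason remains contradicted, SAE reporting supplies seriousness and not severity, and that reporting itself depends on events coming to notice.

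**Conclusion.** The point holds as an internal contradiction with a limited practical consequence. The ground for waiving severity grading is refuted within Section 11.0 and again in Section 7.0. The consequence is that non-serious and borderline events carry no grade, so severity trends cannot be seen at the annual review.

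Events are also likely to be less closely observed in the ADF-only and control arms. That rests on 115 to 120 watched sessions per compliant participant in the exercise arms against none, and on the absence of any described common inquiry about events. It is an inference from opportunity. It assumes that staff who watch a session notice and record what happens, and that no unseen form already asks all arms the same question. The size of any resulting bias cannot be computed from the documents. It would matter only if harms were compared by arm, which the plan does not currently propose.

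**What to change.** In Section 11.0, delete the statement that only minor events may occur together with the waiver, and reconcile the paragraph with the cardiac-event and SAE text in Sections 7.0 and 11.0. Then:

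- record each event with a standard severity grade, seriousness and relatedness;
- ask all four arms the same short event question at contacts they share: at least the week 1, 13 and 24 visits, and with the weekly home weight if that weight is reported to staff, which the protocol does not say;
- tabulate events by arm and grade at each safety review.

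This changes no intervention or clinical rule. It needs a form field, one question and revised wording. The downside is more events on record and some extra review time. At the planned 360 participants, the three visits give 360 × 3 = 1,080 responses, and a weekly question would give 360 × 24 = 8,640, so the weekly option should be chosen with that workload in view.

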## 6.0 Study design and procedures

A 24-week randomized, controlled, parallel-arm feeding trial will be implemented to test the effects of ADF and exercise, alone and in combination, on hepatic steatosis/fibrosis, hepatokines, hepatic insulin sensitivity, and other metabolic disease variables. Obese individuals with NAFLD (n = 360) will be randomized to 1 of 4 groups: (1) ADF (fast day: 25% energy intake, feed day: ad libitum fed, no exercise), (2) exercise (ad libitum fed, training 5 days/week), (3) combination (ADF plus exercise), and (4) control (ad libitum fed, no exercise). Changes in hepatic steatosis will be measured by MRS, and hepatic insulin sensitivity will be assessed by OGTT testing and the Matsuda Index. All study activities will be carried out at the Human Nutrition Research Unit (HNRU) located in the Applied Health Sciences Building ([name]).

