**Control group protocol:** Controls will be instructed to maintain their weight throughout the trial, and not to change eating or physical activity habits. Controls will not receive packaged meals or dietary counseling. Controls will visit the research center at the same frequency as the treatment groups (for outcome measurements) to control for investigator-interaction bias between groups. Controls will be offered free weight loss diet counseling (4 sessions) at the conclusion of the study by [name], MS, RD.

**Subject compensation.** Each subject will receive \$500 upon completion of the trial. Compensation will be prorated (please see Initial Review application for details).

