## Summary of intervention groups and key outcome measures

## Study activities

Study activities	Study visits (week of study)																								
	Screen	1	2	3	4	5	6	7	8	9	10	11	12	13	14	15	16	17	18	19	20	21	22	23	24
Informed consent	•																								
Screening questionnaire	•																								
Michigan Alcohol Screening test	•																								
Pregnancy test	•	•																							•
Body weight (at home)	•	•	•	•	•	•	•	•	•	•	•	•	•	•	•	•	•	•	•	•	•	•	•	•	•
Blood draw	•	•																•							•
Blood pressure/heart rate		•																•							•
Body composition (BIA)		•																•							•
Waist circumference		•																•							•
Body composition (DXA)		•																•							•
Activity monitor		•																•							•
Hepatic insulin sensitivity (OGTT)		•																•							•
Hepatic steatosis (MRS)		•																•							•
Food record	•	•																•							•
Sleep questionnaires		•																•							•
Time per visit:	1	4	0	0	0	0	0	0	0	0	0	0	0	0	0	0	0	0	0	0	0	0	0	0	4

**Body weight, blood pressure, heart rate:** Body weight measurements will be taken weekly with subjects wearing light clothing and without shoes using a balance beam scale at home. Digital scales will be provided to each subject. Height will be assessed using a wall-mounted stadiometer at week 1. BMI will be assessed as kg/m^2. Blood pressure and heart rate will be assessed at week 1, 13, 24.

**Body composition:** Dual energy X-ray absorptiometry (DXA) will be performed on all subjects at week 1, 13, and 24 (iDXA, GE Inc) to assess fat mass, fat free mass, and visceral fat mass. Percentage body fat will be assessed in triplicate using a tetra-polar bioelectrical impedance analyzer each week (Omron HBF-500; Omron Health Care, Bannockburn, IL). Waist circumference will be measured weekly.

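### Section 11.0 plans a cumulative review of harms only once a year against a 24-week treatment; a 13-week tally by arm would cut the longest wait for an event to be counted from 52 weeks to 13

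*Combined protocol and SAP*

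**What the plan says.** **Cumulative review.** Section 11.0 sets the frequency: "Safety reviews will be conducted annually in conjunction with the protocol renewal to OPRS." It also assigns the task: "The PI will be responsible for reporting any adverse events and conducting the annual safety review of study data." Treatment length comes from Section 6.0: "A 24-week randomized, controlled, parallel-arm feeding trial will be implemented to test the effects of ADF and exercise."

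**Single-event routes.** Sections 11.0 and 13.3 send SAEs to OPRS within 48 hours, and incidents or problems within 10 working days. Fatal or life-threatening SAEs and unanticipated problems go to NIH within 7 calendar days, and unanticipated problems that raise the known risk within 30. Section 11.0 adds: "The OPRS will be notified of any adverse events as described above." There is a 24-hour phone line. Under Section 7.0 an injured exerciser stops and stays out of training until the pain eases. Under Section 13.3 participants whose laboratory risk values worsen are told.

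**Other relevant text.** The PI's weekly check in Section 10.0 concerns data quality (assay output and questionnaire responses). Section 8.0 does not list adverse events among the data sources, and Section 12.0 plans no summary of them. Section 11.0 uses no grading scale.

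**Contact by arm.** In the two exercise arms, "A research assistant will be present to supervise all the training sessions over Zoom," and "Subjects will be permitted to miss 5 sessions total during the 24-week trial." In all arms, "Body weight measurements will be taken weekly with subjects wearing light clothing and without shoes using a balance beam scale at home."

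**The concern.** The trial takes sedentary adults with a BMI of 30.0 to 59.9 from 40 minutes at 65% of maximum heart rate in week 1 to 60 minutes at 85% by week 3, five days a week at home. Half of the exercisers also fast on alternate days. The harms the protocol expects are mostly minor: strains, sprains, hunger and stress. A cardiac event is also named.

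Minor harms seldom say much one at a time. If the training step-up is too steep, or fast-day advice is poor, this shows mainly when events are counted and compared between arms. Under the plan nobody is assigned to do that between annual reviews. A participant who starts just after one review finishes well before the next. At stake is the chance to adjust training or advice while people who started alongside those affected are still being treated.

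A second matter is how evenly events are collected. Staff watch the exercise arms several times a week, but not the other two arms. A count by arm would therefore partly measure observation.

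**Working it through.** The annual frequency is a stated rule, not a derived figure, so there is no calculation of the plan's to reproduce. The check is interval arithmetic.

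**Inputs.** Review interval I = 52 weeks (Section 11.0). Treatment T = 24 weeks (Section 6.0). Proposed interval I = 52/4 = 13 weeks.

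**Formulas.** For one event, the longest wait to the next review is I. The mean wait is I/2 if events are evenly spread between reviews.

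| | Annual | Every 13 weeks |
|---|---|---|
| I/T | 52/24 = 2.17 | 13/24 = 0.54 |
| Longest wait, one event | 52 weeks | 13 weeks |
| Mean wait, one event | 26 weeks | 6.5 weeks |
| Mean wait as share of treatment | 26/24 = 108% | 6.5/24 = 27% |

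**Coverage of a participant's own treatment.** Under the annual rule, someone who starts just after a review finishes 52 − 24 = 28 weeks before the next. With a 13-week interval, everyone treated for the full 24 weeks has at least one review during treatment, whatever the enrolment pattern, because 13 < 24.

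**The 52 weeks is an upper bound.** If enrolment opens g weeks after approval, the first review falls 52 − g weeks after the first participant starts. The protocol does not give g.

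**Observation by arm.** Exercise arms: 5 × 24 = 120 supervised sessions, or 120 − 5 = 115 with the allowed misses. The other arms clearly have fewer scheduled contacts, but the number cannot be fixed:

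- Outcome assessments fall at weeks 1, 13 and 24.
- Section 6.0 has blood drawn on consecutive feed and fast days. Section 7.0 counts 18 samples, or 18/3 = 6 per time point. The glucose tolerance test uses 1 + 4 = 5, so the sixth suggests about two visit days per time point.
- ADF participants receive fast-day meals in weeks 1 to 4 and meet a dietitian at week 5.
- The text has body fat and waist measured weekly, while the activities table does not.
- The coordinator makes a COVID screening call before each campus visit.

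The activities table has no adverse-event row for any arm.

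**The case against.** The best defence is that annual review suits the stated risk. Section 11.0 calls the risk of significant events low, and most expected harms are anticipated and disclosed. Every adverse event reaches the PI, who could notice a cluster and must report an unanticipated problem of greater risk within 30 days. OPRS and NIH requirements, which the documents cite but do not reproduce, may ask for more. Earlier annual reviews also protect later entrants. All of this stands as a limit on severity. None of it assigns anyone to count events by arm between annual reviews.

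Several stronger readings are tempting but not supported:

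- *Harms go unwatched for a year.* They do not; the single-event routes operate throughout.
- *A pattern stays hidden for 52 weeks, or 26 on average.* Those figures describe one event. A run builds up over time, so the wait from when it becomes recognisable is shorter, and a run that straddles a review is partly seen at that review.
- *The weekly question shortens the wait.* Only the review schedule does that.
- *Participants who do not exercise are seen only three times.* The text points to more visit days than that.
- *No one asks about harms.* A missing table row does not prove this.
- *A given share of participants, or number of new starters, misses a review.* That needs an enrolment rate, and none is given.

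It is also fair to say that early tallies will be small, and that self-reports from people who know their arm will pick up ordinary aches and colds. The tally should therefore be descriptive.

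**Conclusion.** The point holds as a design choice that should be improved; it is neither an error nor a contradiction in the plan. The only planned cumulative review of harms comes at intervals of more than twice the treatment length. A non-serious event can wait up to 52 weeks to be counted with others. The mean is 26 weeks, which assumes evenly spread events. A 13-week schedule reduces these to 13 and 6.5 weeks. The maxima follow from the schedule alone.

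No event rate is given, so no number of harms averted can be claimed. Uneven observation between arms is a separate, secondary weakness. Its direction is clear, but its size is not established.

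**What to change.** **Main change, Section 11.0.** Replace the frequency rule with wording such as: *At least every 13 weeks the PI will review a descriptive cumulative tally of all adverse events and SAEs by arm, shown as participants with at least one event per participant started. Concerning patterns will be referred to OPRS by the existing reporting route. A summary will accompany the annual protocol renewal.*

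**Secondary change, for comparability only.** Add one row to the activities table, weeks 1 to 24, all four arms, attached to the weekly home weight: *In the past 7 days, have you had any injury, pain, illness or other new health problem? If yes, what was it, and did it stop your usual activities or lead you to seek medical care?* Compare arms on these answers, and list events seen only over Zoom separately. Exercise versus no-exercise counts still need caution, because the exercise arms remain more closely observed.

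**Cost.** The PI holds four reviews a year instead of one. The question yields at most 360 × 24 = 8,640 short answers over the trial, or 180 × 24 = 4,320 if the 45 per arm in the Section 6.0 intervention table is right. The protocol does not say how home weights reach staff, so a weekly e-mail or phone report is assumed, and positive answers will need some follow-up. Early counts will be small, and there is some risk of reacting to a chance cluster. No committee or stopping boundary is needed.
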